6.9.4 Quality of Life Studies to be Performed

- (1) FACT-Lymphoma subscale (FACT-Lym) - 42 items.
- (2) FACT-Fatigue scale - 13 items.
- (3) FACT/GOG-Neurotoxicity scale - 11 items.

6.9.5 Administration Instructions

- 6.9.5.1 The questionnaires must be administered at the time points listed above. The patient should be instructed to respond to the questionnaires in terms of his/her experience during the time frame specified on each questionnaire.
- 6.9.5.2 The patient should be asked to read the instructions at the beginning of each questionnaire and complete all the items. It is permissible to assist the patient with the completion of the questionnaires as long as the staff person does not influence the patient's responses.
- 6.9.5.3 The questionnaires must be reviewed by the protocol nurse or research coordinator as soon as the patient completes them to ensure all items were marked appropriately. If more than one answer was marked, the patient should be asked to choose the answer which best reflects how he/she is feeling. If a question was not answered, the patient should be asked if he/she would like to answer it. The patient should always have the option to refuse. If the patient refuses, it should be indicated on the questionnaire that he/she declined to answer the item.
- 6.9.5.4 If the patient cannot complete a questionnaire, or if the patient refuses to complete the questionnaire, the reason should be noted on the questionnaire. .

- 6.9.5.5 If a patient misses an appointment on the scheduled date, the questionnaires may be completed by telephone on the appointed date or they may be completed at the time the appointment is rescheduled. If the missed scheduled date is on a treatment date, the quality of life assessment will be done when the patient comes for the rescheduled treatment.
- 6.9.5.6 If a patient cannot complete the questionnaire because he/she is too sick, this should be documented on the questionnaire. .

7 STUDY PARAMETERS

7.1 Schedule of Study Activities. See *Table 4 below* for the Study Activities.

- 7.1.1 **Pre-cycle testing.** Laboratory assessments must be done within 30 days before beginning study treatment (testing may be completed on day 1 of each cycle, but must be done prior to treatment). Measurements of measurable disease (as in Section 6.1.1) or non-measurable disease (as in Section 6.1.2) must be completed within 60 days prior to starting treatment. Staging bone marrow and cardiac testing (e.g., echocardiogram) may have been done within the prior 90 days before starting treatment. A window of +/- 2 days is permitted for all scheduled visits, tests, and procedures.
- 7.1.2 **Treatment Schedule.** Patients will be seen by a physician every 3 weeks during the SGN-35 “lead in” phase, every 4 weeks during AVD therapy, and every 3 weeks during SGN-35 consolidation. A window of +/- 2 days is permitted for all scheduled visits, tests, and procedures.
- 7.1.3 **Follow-Up Visit Schedule.** Patients with CR, PR, or SD will return for a follow-up examination 30 days after their last treatment dose. Early termination patients and patients with PD will return for a final study visit (including imaging) 30 days after their last respective treatment dose.
- 7.1.4 **Concomitant Medications.** All concomitant medications will be recorded from screening through study discontinuation.
- 7.1.5 **Eastern Cooperative Oncology Group (ECOG) Performance Status Assessment.** The patient’s ECOG performance status will be assessed during screening (within 14 days before beginning study treatment). To be eligible for enrollment, patients must have a score of 0, 1, or 2, according to the ECOG scale (see Appendix I).
- 7.1.6 **CT scan and PET scan.** Patients will undergo CT scans of the chest, abdomen and pelvis +/- neck and FDG-PET scanning prior to cycle 1. Scans must be done within 60 days prior to day 1, cycle 1. The baseline CT scan may be done concurrently with the PET scan, however oral contrast needs to be used (use of intravenous contrast for the diagnostic CT is encouraged, but not mandatory).

Table 4. Schedule of Activities.

Parameter	Pre-study	SGN-35 lead-in Cycles¹	AVD¹⁵ Cycles²	SGN-35 consolidation¹⁵ Cycles³	Post-Therapy Follow-up
Assignment of IPS score	X				
History and Physical examination	X	X	X	X	X ¹³
Performance Status	X	X	X	X	X ¹³
Tumor Measurements by Physical Exam (if applicable)	X	X	X	X	X ¹³
CBC and Differential ⁴	X	X	X	X	X ¹³
Serum Chemistries (electrolytes, SGOT, SGPT, total bilirubin, direct bilirubin, ⁵ LDH, creatinine, glucose, alkaline phos, and calcium)	X	X	X	X	X ¹³
Serum amylase and lipase ¹⁷	X	X		X	
ESR	X	X	X	X	
Uric acid ¹⁶	X				
Bone marrow biopsy (bilateral preferred, unilateral acceptable) ⁶	X				
EBV PCR ¹⁶	X		Day 1, cycle 1	On start of cycle 1	At end of and 6 months after consolidation
TSH and Hemoglobin A1c ¹⁶	X			On start of cycle 1	
HIV screening ⁷	X				
Echo or MUGA	X		X ⁸		
CT Chest, Abdomen, and Pelvis ^{9, 10, 15}	X	X	X ¹⁵	X ¹⁰	X ¹³
PET/CT Scan ^{9, 10}	X	X	X		
Co-morbidity/ADL assessment ¹¹	X				X ¹¹
Quality of life assessments ¹²	X		X	X	X
SGN-35 PK sample ¹⁸		X			

Correlative science blood studies ¹⁴				
	X	X	X	X
1. Two cycles of therapy given 21 days apart (+/- 7 days). Patients may be evaluated in the office more frequently, if needed, at physician discretion. If there is documented progressive disease after SGN35 (i.e., prior to initiation of AVD), patients may still remain 'on trial' and proceed to AVD chemotherapy, however they will not receive SGN35 consolidation. Study visits, tests, and procedures should be completed Day 1 (+/- 2 days) of each cycle.				
2. Six cycles of therapy. Cycles are every 28 days (+/- 7 days), though treatments are given day 1 and day 15 of each cycle. Patients may be evaluated in the office more frequently, if needed, at physician discretion. Study visits, tests, and procedures should be completed Day 1 (+/- 2 days) of each cycle.				
3. Four cycles of therapy. Cycles are every 21 days (+/- 7 days). Patients may be evaluated in the office more frequently, if needed, at physician discretion. Study visits, tests, and procedures should be completed Day 1 (+/- 2 days) of each cycle.				
4. CBC at baseline and as clinically indicated to capture nadir: please record the absolute lymphocyte count.				
5. Direct bilirubin is recommended, but required only if total bilirubin is elevated.				
6. Baseline bone marrow biopsy is mandatory within 90 days prior to starting treatment. Repeat bone marrow biopsy at time of CR and relapse ONLY if positive at baseline (bilateral biopsy is preferred, but unilateral is acceptable). .				
7. Not mandatory, but recommended.				
8. Repeat after 4 th cycle of AVD. May be repeated earlier or more frequently as clinically indicated.				
9. Combined PET/CT scan will be sufficient if the PET/CT is performed with oral contrast (intravenous contrast is encouraged, but not mandatory); if PET/CT is without oral contrast, then separate/dedicated CTs of chest/abdomen/pelvis (in addition to PET/CT) must be obtained. Please see Section 6.6 for further guidelines on recommended interpretation of PET scans.				
10. The first 22 evaluable patients entered on the study will have a repeat FDG-PET after the 2 "lead in" cycles of SGN35. This should be completed the week prior to planned initiation of AVD chemotherapy. All patients entered on study will have FDG-PET and CTs performed prior to day 1 of cycle 4 of AVD therapy (after day 15 of cycle 3). Thereafter, once a patient enters complete remission (CR), then only CT's (chest/abdomen/pelvis) should be obtained (not both PET/CT and dedicated CTs). All patients will have re-staging scans performed at the end of AVD chemotherapy (i.e., prior to start of SGN35 consolidation therapy).				
11. See Appendix III and Appendix IV for further details/methods for completion. This includes Co-morbidity assessment (Appendix III) and Activity of Daily Living (ADL) assessment (Appendix VI). Obtain once at baseline (pre-treatment) and then repeat once at the completion of all therapy.				
12. See Section 6.9 for exact timing and description and Appendix IV for Quality of Life forms.				
13. 30 days (+/- 2 days) after the last dose of treatment, patients should have repeat re-staging CTs +/- FDG-PET completed. Thereafter, the follow-up schedule will be office visits with blood tests q 3 months and re-staging CTs q 6 months for 3 years, then per local institutional guidelines. Patients who stop treatment early due to AEs or PD will also follow this schedule.				
14. See Table 4 in Section 12.3.3 for full explanation of which blood tubes (i.e., ACD/yellow, EDTA/purple, and red top) and timing (e.g., baseline/pre-SGN35, after 2 cycles of SGN35 lead-in, and after completion of AVD chemotherapy) of correlative blood studies.				
15. Any patient who has not achieved a CR or PR after the 6 cycles of AVD should be taken off study and not proceed with SGN consolidation therapy. However, patients who do not complete 6 cycles of AVD (due to toxicity: designated 'chemotherapy intolerable'), but achieve PR or CR may proceed with SGN35 consolidation therapy. See Section 5.3.3.8 regarding designation of chemotherapy intolerance. Patients who are designated as 'chemotherapy intolerant' should have restaging CTs of the chest, abdomen, and pelvis performed prior to the start of SGN35 consolidation (if they have not been performed within the preceding 30 days).				

16. Encouraged, but not required.
17. Amylase and lipase levels must be drawn 72 hours prior to the dosing of SGN-35. See **Section 5.2.5.1** regarding dose modifications for pancreatitis.
18. 2.7 mL of whole blood to be collected in a 3 mL Na Citrate (blue top) tube 48-72 hours post the first dose of SGN-35. The properly frozen plasma should be shipped overnight to the Lurie Cancer Center Pathology Core Facility. Should an unexpected SAE arise with a dose/cycle of SGN-35 **other than the 1st dose/cycle**, samples should be drawn and sent on a case-by-case basis to the Lurie Cancer Center Pathology Core Facility. This should be discussed with the study P.I & QAM. See section 12.4 for specimen processing and storage requirements.

8 DRUG FORMULATION AND PROCUREMENT.

8.1 SGN-35.

8.1.1 **Other names.** Brentuximab vedotin.

8.1.2 **Classification.** SGN-35 is an antibody-drug conjugate consisting of the anti-CD30 antibody cAC10 conjugated to MMAE, an anti-tubulin agent.

8.1.3 **Mode of Action.** Induction of apoptosis and cytotoxic cell death.

8.1.4 **Storage and stability.** SGN-35 is supplied as sterile, preservative-free, white to off-white lyophilized cakes for reconstitution for IV administration and are supplied by Seattle Genetics in single-use glass vials. Each vial of SGN-35 product contains SGN-35, trehalose, sodium citrate, and polysorbate 80.

Vials containing study treatment must be refrigerated at 2–8°C in a secure location (e.g., locked room) accessible only to the pharmacist, the investigator, or a duly designated person. Study treatment does not contain preservatives; therefore, opened and reconstituted vials of study treatment must be used on the same day when stored under refrigeration at 2–8°C. Reconstituted SGN-35 should not be stored at room temperature. It is recommended that study treatment vials and solutions be protected from direct sunlight until the time of use. Reconstituted vials must not be shaken.

8.1.5 **Dose specifics.** Dosing is based on patient weight according to the institutional standard; however, doses will be adjusted for patients who experience a $\geq 10\%$ change in weight from baseline. Actual weight will be used except for patients weighing greater than 100 kg; dose will be calculated based on 100 kg for these individuals. The dose will be rounded to the nearest whole number of milligrams.

8.1.5.1 Dosing for the first 2 cycles of the SGN-35 lead-in are administered at 1.8 mg/kg given 3 weeks apart.

8.1.5.2 Dosing for the 4 cycles of consolidation (i.e., after induction AVD chemotherapy), SGN-35 dosing is 1.8 mg/kg or 1.2 mg/kg given every 3 weeks apart for 4 doses. See **Section 5.4.2** for details.

8.1.5.3 For SGN-35 dose modifications, see **Sections 5.2.5 and 5.4.3** as well as Table 2.

8.1.6 **Preparation.** Procedures for proper handling and disposal of anticancer drugs should be considered. Several guidelines on this subject have been published (see manufacturer's prescribing information insert). Use appropriate aseptic technique for reconstitution and preparation of dosing solutions.

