Patients 23 through 45 are not required to have a restaging PET or CT scan after the first 2 ‘lead in’ cycles of SGN35. PET and/or CT scans may be obtained at the investigators discretion at this time point. If there is documented progressive disease after SGN35 (i.e., prior to initiation of AVD), patients may still remain ‘on trial’ and proceed to AVD chemotherapy, however they will not receive SGN35 consolidation.

5.2.8.2 Re-staging for chemotherapy intolerant patients.

See Section 5.3.3.8 for this definition. Chemotherapy intolerant patients may proceed with consolidation SGN35 therapy if they have achieved either a PR or CR at time of chemotherapy intolerant designation. These patients should have repeat staging CT scans performed prior to initiation of SGN35 consolidation therapy (if not done within the preceding 30 days).

5.3 AVD chemotherapy.

5.3.1 Dosing.

Chemotherapy	Dose	Infusion	Timing
Doxorubicin (adriamycin)	25 mg/m ²	IV	Days 1 and 15
Vinblastine (velban)	6 mg/m ²	IV	Days 1 and 15
Dacarbazine	375 mg/m ²	IV	Days 1 and 15

(DTIC)			
--------	--	--	--

NOTE: A cycle is 28 days. Use actual weight to calculate body surface area. For further information regarding drug administration, please see Section 8.2.

5.3.2 Number of cycles.

Patients will receive 6 cycles of AVD chemotherapy, unless judged by the treating physician to be chemotherapy intolerant (see section 5.3.3.8). Each cycle is scheduled to be repeated every 28 days.

5.3.3 Dose modifications.

NOTE: All toxicities should be graded according to the CTC (version 4.0).

5.3.3.1 Hematologic Toxicity.

Dose delays and reductions of AVD chemotherapy only are to be done at the discretion of the treating physician and must be clearly documented on the Treatment eCRF in NOTIS along with the CTC (version 4.0) grade. Delays of greater than 3 weeks due to AVD toxicity must be approved by the PI and the QAM must be included on this correspondence. The following are only recommendations (are not mandatory) for modifications for AVD; SGN modifications are mandatory and are described above in Table 3. Some guidelines to be considered are for absolute neutrophil count of <500 on the day of treatment would be to consider addition of G-CSF (filgrastim) therapy. This is strongly preferred due to the long half-life of pegfilgrastim.

Patients with persistent severe neutropenia, especially despite use of granulocyte growth factor, could have reduction of doxorubicin and vinblastine by 25%.

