5.3.3.2 Hepatic Dysfunction

Reduce the dose of vinblastine and doxorubicin as follows*:

Bilirubin	% of full dose**
=/< 1.5	100
> 1.5 but < 3.0	50
=/> 3.0 but < 5.0	25
=/> 5.0	0

*Gilbert's syndrome is excluded from this guideline;

**May give full dose with recovery of bilirubin < 1.5.

5.3.3.3 Peripheral Nervous System Toxicity (Vinblastine).

Vinblastine may be dose reduced at the discretion of the treating physician. Consideration for dose reduction (e.g., by 50%) should

be given for grade 2 neuropathy (i.e., limiting instrumental ADL), especially if pain is present. Vinblastine should be stopped for grade 3 neuropathy (i.e., limiting self care ADL). If neuropathy improves, re-escalation may be considered.

NOTE: Instrumental ADL refers to preparing meals, shopping for groceries or clothes, using the telephone, managing money, etc. Self care ADL refers to bathing, dressing and undressing, feeding self, using the toilet, taking medications, and not bedridden.

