10.4 Scheduled Assessment of Safety

- 10.4.1 Safety Data: Safety data will be collected on Day 1 of each cycle of chemotherapy and then at 3 month intervals for a total of 24 months. Analysis will also include MUGA scan studies done at baseline.
- 10.4.2 Efficacy endpoints: Efficacy endpoints data will be analyzed (primarily: CT scans and PET scans) at baseline and after 3 cycles of the above regimen and at completion of chemotherapy; and then every 3 to 6 months for 2 years total.

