Eligibility Checklist	X														
On-Study Form		X													
Concomitant Medications Form		X ¹	X ⁵	X ⁵						X ⁵					
Patient Vitals Form			X ³	X ³						X ³				X ¹¹	
Labs Order Form			X ³	X ³						X ³				X ¹¹	
AE Form		X ²	X ⁴	X ⁴						X ⁴				X ¹¹	
Treatment form			X ⁶	X ⁶						X ⁶					
Bone Marrow Biopsy Report Upload		X ⁷													
CIRS Form Upload		X												X ¹³	
FACT/GOG Neurotoxicity Upload		X				X ¹²			X ¹²			X ¹⁵		X ¹³	X ¹⁶
FACT-Lymp and FACT-fatigue upload		X				X ¹²			X ¹²			X ¹⁵		X ¹³	X ¹⁷
ADL Assessment	X ²⁰												X ²⁰		
PET/CT Data Form Upload	X			X ⁸			X ⁹			X ¹⁰			X ¹³	X ¹⁸	
Cheson Assessment Form				X ⁸	X ⁷		X ⁹			X ¹⁰			X ¹³	X ¹⁸	
Off-Treatment Form													X ¹⁴		

Follow-Up Form	X ¹⁹
----------------	-----------------

- 1 Should reflect medications taken at baseline
- 2 Should reflect all AEs present at baseline
- 3 Enter by end of each cycle, for assessments conducted on D1 of each cycle.
- 4 Update after each physical exam and labs done on D1 of each cycle, and as needed.
- 5 Update as required
- 6 To be entered at the end of each cycle
- 7 Should reflect bmbx results required at baseline. If bmbx is positive at baseline, repeat biopsies should be done, and reports uploaded at time of CR and relapse.
- 8 Upload completed forms after end of SGN lead-in cycle 2, PET/CT Data Form only for the first 22 patients.
- 9 Upload completed forms by at the end of cycle 3 (for assessment required C3D15).
- 10 Uploaded completed forms for assessment required at the end of AVD therapy.
- 11 Enter q 3 months for a period of three years after pt completes therapy.
- 12 Submit by end of C1 and C4 for assessments conducted at D1 of C1 and C4.
- 13 To be completed and uploaded at the end of consolidation.
- 14 To be completed 1 week within 1 week of when subject goes off-treatment.
- 15 To be completed and uploaded by the end of C1 of consolidation.
- 16 To be completed and uploaded 6 months and 12 months after completion of consolidation.
- 17 To be completed and uploaded 12 months after the completion of consolidation.
- 18 To be completed and uploaded q 6 months for a period of 3 years.
- 19 Complete follow-up form for a period of 3 years after pt goes off treatment.
- 20 Print physician's assessment of ADLs (appendix VI) and upload into the eCRF system.

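### Day 15 AVD doses (6 of 12 planned) have no scheduled CBC or chemistry and no required lab eCRF entry, so the laboratory toxicity summary in 9.6.1 rests mainly on Day 1 values during AVD

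*Combined protocol and SAP*

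**What the plan says.** **Dosing.** Section 5.3.2 states: "Patients will receive 6 cycles of AVD chemotherapy, unless judged by the treating physician to be chemotherapy intolerant". Section 5.3.1 and Table 4 footnote 2 give two treatment days per 28-day cycle: "Cycles are every 28 days (+/- 7 days), though treatments are given day 1 and day 15 of each cycle".

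**Testing, visits and recording.** Four provisions set the timing during AVD:
- Table 4 footnote 2: "Study visits, tests, and procedures should be completed Day 1 (+/- 2 days) of each cycle".
- Section 7.1.2: patients see a physician "every 4 weeks during AVD therapy".
- Section 10.4.1: "Safety data will be collected on Day 1 of each cycle of chemotherapy".
- Appendix VIII, data submission table, footnote 3, attached to the laboratory and vitals forms: "Enter by end of each cycle, for assessments conducted on D1 of each cycle".

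**Guidance that uses laboratory values.** Section 5.3.3.1 says that a guideline for an "absolute neutrophil count of <500 on the day of treatment would be to consider addition of G-CSF (filgrastim) therapy". The same section describes the AVD hematologic items as recommendations that are not mandatory. Section 5.3.3.2 says "Reduce the dose of vinblastine and doxorubicin as follows" and gives bilirubin bands. Section 5.3.3.6 gives creatinine clearance bands for dacarbazine. Neither 5.3.3.2 nor 5.3.3.6 states a day of measurement.

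**Analysis.** Section 9.6.1 summarises blood counts, liver tests, bilirubin and creatinine descriptively and by CTCAE grade.

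**The concern.** The guidance in 5.3.3 relies on laboratory values, and in the case of the neutrophil count on the value at the treatment day. The schedule provides such values for only one of the two treatment days in each AVD cycle. A site that follows Table 4 and Appendix VIII literally would have no routine laboratory value at Day 15. A site that draws blood on Day 15 anyway is not required to enter the result.

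The safety of the sequential regimen is a secondary objective (2.2), and the background in 1.4 stresses chemotherapy toxicity in older patients. What is at stake is whether the 9.6.1 tables describe laboratory toxicity during AVD completely.

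**Working it through.** The documents state no figure for this point, so there is none to reproduce. The check is a direct count and a comparison of sections.

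**Step 1. Count of doses.** Inputs are 6 AVD cycles (5.3.2), 2 treatment days per cycle (5.3.1, Table 4 footnote 2) and 1 scheduled test day per cycle (Table 4 footnote 2).
- Planned AVD doses: 6 × 2 = 12.
- Doses with a scheduled test: 6 × 1 = 6.
- Doses without one: 12 − 6 = 6, and 6/12 = 50%.
- If every patient completed 6 cycles, this would be 45 × 6 = 270 of 540 doses in the 45 evaluable patients, or 48 × 6 = 288 of 576 in the 48 enrolled. These are upper limits, because some patients will stop AVD early.

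**Step 2. Can a visit window reach Day 15?** Day 1 plus 2 days ends at Day 3. The next Day 1 falls nominally on Day 29, so its window opens on Day 27. With the full 7-day shortening of a cycle it falls on Day 22 and its window opens on Day 20. Day 15 lies outside both.

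**Step 3. Treatment days that can show an AVD effect.** Cycle 1 Day 1 precedes any AVD. The remaining AVD treatment days are Day 15 of cycles 1 to 6 (6 days) and Day 1 of cycles 2 to 6 (5 days), 11 in all. Only 5 of the 11 have scheduled tests. The first is cycle 2 Day 1, after two AVD doses.

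**Step 4. Does another provision close the gap?**

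| Provision | Covers Day 15? |
|---|---|
| Table 4 footnote 4 | CBC only, when clinically indicated; no fixed day |
| Table 4 footnote 2, extra office evaluation | At physician discretion |
| Drug sections 8.2.12, 8.3.12, 8.4.11 | Advise CBC and platelet monitoring; no days given |
| Appendix VIII footnote 4, adverse event form | Yes, updated as needed |
| 5.3.3.1, treatment form | Yes, for a delay or reduction, with its CTC grade |
| 10.3.3.1, SAE reports | Yes, within 24 hours of awareness |
| Appendix VIII footnote 3, laboratory form | Day 1 assessments only |

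Toxicity that becomes an adverse event, or leads to a delay or reduction, has a route into the database. A Day 15 laboratory value as such has no required route.

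**Step 5. Direction of the effect on 9.6.1.** Assume that the table shows each patient's worst grade, which 9.6.1 does not specify. The worst grade over Day 1 values alone cannot exceed the worst grade over Day 1 and Day 15 values together. The error can therefore only be an under-count. Its size cannot be derived from the documents.

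**The case against.** The strongest case against the point has four parts.

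1. **Toxicity on Day 15 is not invisible.** Section 10.2.1 counts an abnormal laboratory finding as a possible adverse event, and the adverse event form is not confined to Day 1. Delays and reductions on any dose day must be documented with a grade. The Appendix VIII text lists the laboratory form after each cycle without a Day 1 limit, and footnote 3 does not bar other values. This stands. A reader might infer that nothing about Day 15 toxicity is recorded; the documents do not support that.

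2. **The guidance is softer than a dose rule tied to each treatment day.** The hematologic items are not mandatory, the quoted neutrophil guideline concerns considering G-CSF, and only that guideline names the treatment day. This also stands. What remains is that a guideline using the treatment-day count assumes a value that the schedule does not provide for on Day 15.

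3. **The loss is in frequency, not in time since dose.** From cycle 2, a nominal Day 1 draw comes 14 days after the previous Day 15 dose, the same interval as a Day 15 draw after Day 1. Section 8.2.11 puts the doxorubicin nadir at 10 to 14 days. This is fair, and it limits the point: the scheduled draws sample a relevant time, but only 5 of 11 times.

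4. **AVD is not being compared with SGN-35.** A reader might contrast full laboratory coverage of SGN-35 doses with half coverage of AVD doses and infer biased regimen tables. But 9.5.1 tabulates adverse events, whose collection is not limited to Day 1, and 9.6.1 plans no comparison between the phases. Coverage of doses is also not a detection rate. Turning it into one would need a per-draw toxicity probability and a within-patient dependence that the documents do not give.

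**Conclusion.** The point holds in limited form. For 6 of 12 planned AVD doses (50%) the protocol schedules no CBC or chemistry and requires no laboratory form entry, apart from discretionary CBCs. The four timing provisions agree with each other, so this is not a slip in one footnote, but they do not fit the guidance in 5.3.3.

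The consequence is confined to safety description. The 9.6.1 summary would rest mainly on Day 1 values during AVD and can under-count laboratory toxicity by an amount that the documents do not allow one to estimate. Adverse event forms, SAE reports and treatment form entries recover part of it. The two-stage decision on CR does not use these laboratory values.

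The conclusion assumes that sites follow Table 4 and Appendix VIII as written. If sites already draw blood at each infusion visit, the scheduling gap matters less in practice, but the lack of required data entry remains.

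**What to change.** The sponsor should reconcile 5.3.3 with Table 4 footnote 2, 7.1.2, 10.4.1 and Appendix VIII footnote 3, so that the guidance, the schedule and the forms agree. How they are reconciled clinically is for the sponsor; no testing schedule, threshold or dose rule is proposed here.

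On the data side, extend Appendix VIII footnote 3 so that laboratory values obtained at Day 15 AVD doses are entered on the laboratory form, and state in 9.6.1 that they are included in the summary. For patients already treated, enter the Day 15 values that are available, or report the limitation alongside the tables.

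The cost is an amendment to the text and form instructions, and extra data entry for up to 6 further sets of values per patient.

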Section 5.2.5 (Dose Modifications), including Table 3	Did not include dose modifications specifically related to pancreatic toxicity.	Add dose modifications specifically related to pancreatic toxicity (SGN-35 is to be held until the toxicity resolves).	This is being done for patient safety, after a severe, unexpected case of pancreatitis was seen on the study.
Section 7.0 (Study Parameters)	Did not require amylase or lipase testing.	Amylase and lipase testing was added.	This is being done for safety, due to the pancreatitis case seen on the study. These labs will be used for monitoring for toxicity.
Section 7.0 (Study Parameters); Section 12.0 (Pathology Requirements)	Safety PK specimens were not collected.	Safety PK sample collection has been added.	This is being added as a safety measure in the event a study participants

			experiences an adverse drug reaction.
Section 7.0 (Study Parameters) & Table 4 (Schedule of Activities)	
 1. No windows given for scheduled tests, assessments, and procedures. 2. Table listed tests as being completed “every cycle.” 	
 1. Allows a window of +/- 2 days for all scheduled tests, assessments, and procedures. Allows a window of +/- 7 days between cycles. 2. Changed to “X” with footnotes clarifying “Day 1 (+/- 2 days) of each cycle.” 	
 1. Added to avoid protocol deviations for slight changes in scheduling due to weekends, holidays, etc. 2. Clarity
Section 11.0 (Records To Be Kept)	Required treatment eCRFs, including the summary, to be completed at the end of therapy.	Summary eCRFs are no longer required. Treatment data must now be submitted each cycle.	DMC requires more frequent review of data for compliance and safety. In addition, the new eCRFs negate the needs for a treatment summary sheet, as all data is collected on treatment forms.
Amendment 6 – July 30, 2013 Scientific Review Committee Approval – August 7, 2013			
Section(s) Affected	Prior Version	Amendment 6 Changes	Rationale
1.6.5 (Pancreatitis and SGN-35)	Information regarding SGN-35 and pancreatitis based on data available as of May 9, 2013.	Updates data based on more recent internal review of	Updated for safety reasons per memo from

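### Table 4 footnotes 1–3 let a cycle start up to 7 days early (SGN-35 at 14 days, AVD at 21 days), earlier than the dosing text or background supports; a -2/+7 day window would fix this

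*Combined protocol and SAP*

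**What the plan says.** The windows are in the footnotes to Table 4 of the combined protocol and SAP (section 7).

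- **Footnote 1, SGN-35 lead-in:** "Two cycles of therapy given 21 days apart (+/- 7 days".
- **Footnote 2, AVD:** "Cycles are every 28 days (+/- 7 days), though treatments are given day 1 and day 15 of each cycle".
- **Footnote 3, SGN-35 consolidation:** "Four cycles of therapy. Cycles are every 21 days (+/- 7 days".

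Each footnote then gives a second, narrower window: "Study visits, tests, and procedures should be completed Day 1 (+/- 2 days) of each cycle". Section 7.1.2 schedules physician visits every 3 weeks in the lead-in, then "every 4 weeks during AVD therapy, and every 3 weeks during SGN-35 consolidation", and adds: "A window of +/- 2 days is permitted for all scheduled visits, tests, and procedures". It names neither dosing nor cycle start.

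The Amendment 5 entry in Appendix VII describes the two windows as separate items. For the wider one it says "Allows a window of +/- 7 days between cycles", and it gives the reason as "Added to avoid protocol deviations for slight changes in scheduling due to weekends, holidays, etc".

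The dosing text has nominal intervals only: a 21-day SGN-35 cycle (5.2.2), SGN-35 at 3-week intervals (5.4.2.1 and 8.1.5.1), and AVD repeated at 28 days (5.3.2). None of these carries a tolerance or a rule about early dosing.

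**The concern.** A symmetric window treats an early cycle as no different from a late one, although the risks differ. A late start for a holiday costs little. An early start shortens recovery between cytotoxic doses in patients aged 60 or over. Under the footnotes as written, a site could give SGN-35 14 days after the previous dose, or start an AVD cycle 7 days after the day-15 dose, and record either as within window.

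The background does not cover the SGN-35 case. Section 1.6.3 identifies 1.8 mg/kg as the maximally tolerated dose on a 21-day cycle, and the pivotal phase II study used the same dose every 3 weeks. It has no data on 1.8 mg/kg every 14 days. For AVD, section 8.2.11 puts the doxorubicin count nadir at 10–14 days, so a dose 7 days after the last one would come before the nadir. Section 5.3.3.1 makes the SGN-35 dose modifications mandatory but leaves the AVD haematologic modifications as recommendations, so the safeguards are weaker for AVD.

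**Working it through.** The plan states no figure to reproduce. The check is interval arithmetic on the stated schedule.

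**Inputs.** SGN-35: 1.8 mg/kg, nominal 21 days, 2 lead-in and 4 consolidation doses (5.1, 5.2.2, 5.4.2). AVD: nominal 28 days, 6 cycles, doxorubicin 25 mg/m² on days 1 and 15, so 50 mg/m² per cycle (5.3.1, 5.3.2). Windows: footnotes 1–3.

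**Formulas.** Shortest interval = nominal interval − early allowance. Weekly dose = dose × 7 / interval. Intensity ratio = nominal interval / shortest interval. Number of intervals = doses (or cycles) − 1.

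| | Nominal | Current, full −7 used | Proposed, full −2 used |
|---|---|---|---|
| SGN-35 interval | 21 days | 21 − 7 = 14 days | 21 − 2 = 19 days |
| SGN-35 weekly dose | 1.8 × 7/21 = 0.60 mg/kg | 1.8 × 7/14 = 0.90 mg/kg | 1.8 × 7/19 = 0.663 mg/kg |
| SGN-35 intensity | – | 21/14 = 1.50 (+50%) | 21/19 = 1.105 (+10.5%) |
| First to fourth consolidation dose | 3 × 21 = 63 days | 3 × 14 = 42 days | 3 × 19 = 57 days |
| AVD cycle | 28 days | 28 − 7 = 21 days | 28 − 2 = 26 days |
| Doxorubicin per week | 50 × 7/28 = 12.5 mg/m² | 50 × 7/21 = 16.7 mg/m² | 50 × 7/26 = 13.5 mg/m² |
| AVD intensity | – | 28/21 = 1.33 (+33%) | 28/26 = 1.077 (+7.7%) |
| Cycle 1 day 1 to cycle 6 day 1 | 5 × 28 = 140 days | 5 × 21 = 105 days | 5 × 26 = 130 days |
| Day-15 dose to next day 1 | 29 − 15 = 14 days | 22 − 15 = 7 days | 27 − 15 = 12 days |

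The lead-in has 2 − 1 = 1 interval, consolidation 4 − 1 = 3 and AVD 6 − 1 = 5. The number of doses and the amount per dose do not change in any column.

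**Restaging scan.** Section 5.3.5 recommends the AVD cycle 3 scans on days 22–25. Footnote 10 to Table 4 wants them after day 15 of cycle 3 and before cycle 4 day 1. If cycle 3 lasts 21 days, cycle 4 day 1 falls on day 22, so no day in the recommended range precedes it. A scan between days 16 and 21 would satisfy footnote 10 but miss the recommended timing. With a 26-day minimum, cycle 4 starts on day 27 at the earliest and days 22–25 fit.

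**The two windows side by side.** The 7 days apply to the interval between cycles. The 2 days apply to visits, tests and procedures, and the footnotes tie them to Day 1 of each cycle. If Day 1 itself moves forward to day 14, a visit on that day still meets the 2-day rule. Section 7.1.2 does not say what its 3-week and 4-week visits are counted from. Counted from the previous actual visit, its range is 19–23 days for SGN-35 and 26–30 for AVD. On a fixed calendar, a visit 2 days late followed by one 2 days early gives 21 − 4 = 17 and 28 − 4 = 24 days. On either count, a visit at 14 or 21 days is earlier than 7.1.2 taken alone would suggest.

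**The case against.** The strongest reply is that this is a deliberate deviation tolerance. The amendment log introduces the two windows together, for weekends and holidays, and nothing suggests that sites would compress therapy. Other safeguards also apply: the Table 3 holds for SGN-35 toxicity, pre-treatment laboratory tests (7.1.1) and amylase and lipase before each SGN-35 dose (footnote 17). The recommended scan timing itself discourages a 21-day cycle 3. All of this stands and keeps the point minor. But these safeguards respond to toxicity or abnormal results and do not set an interval, the scan affects only one cycle, and a weekend or holiday does not need 7 days on the early side.

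A reader might infer several stronger points that the documents do not support.

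- **That the two windows contradict each other.** They govern different things and can be read together once visits are anchored to the actual Day 1. What remains is an awkward fit with the visit frequency in 7.1.2.
- **That there is no minimum interval.** The −7 itself sets a floor of 14 or 21 days, the dosing sections give fixed nominal intervals, and section 11.6 requires the study to be conducted as described. The accurate statement is that the early side has no limit tighter than 7 days.
- **That patients will receive 50% or 33% more drug per week.** Those increases over a whole phase need the full 7 days at every interval. For the lead-in, with a single interval, a weekly average says little.
- **That 14-day dosing is shown to be harmful.** Section 1.6.3 also reports a weekly-dosing study in which the tolerated dose was exceeded at 1.4 mg/kg. That is a different schedule, and it neither supports nor condemns 1.8 mg/kg every 14 days.

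**Conclusion.** The point holds as a cheap safety improvement of minor severity. Footnotes 1–3 count SGN-35 at 14 days and an AVD cycle at 21 days as within window, while the dosing text gives 21 and 28 days and the background supports 1.8 mg/kg only on a 21-day cycle. An AVD cycle 3 of 21 days would also defeat the recommended scan timing.

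The upper bounds are +50% (SGN-35) and +33% (AVD) in weekly dose intensity, assuming full use of the early allowance and unchanged doses. How often sites would dose early cannot be judged from the documents. The late side is not at issue: the delay rules in 5.2.5, 5.3.3.1 and 5.4.3 concern toxicity, so +7 days remains useful for ordinary scheduling. There is no effect on the complete remission endpoint, the two-stage design or its error rates.

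**What to change.** In Table 4 footnotes 1–3, replace +/- 7 days with -2/+7 days, counted from the previous cycle's actual Day 1. SGN-35 intervals then run from 19 to 28 days and AVD cycles from 26 to 35 days. Record earlier doses as deviations, and leave toxicity delays to 5.2.5, 5.3.3.1 and 5.4.3. The 2 days reuse the tolerance already in 7.1.2. Barring early starts altogether (-0/+7) would also work but is stricter than the concern requires.

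Optionally, add a minimum of 12 days from the day-15 AVD dose to the next day 1. A late day-15 dose would otherwise shorten that gap: given on day 17 and followed by a day-27 start, it leaves 27 − 17 = 10 days. This would be a new rule that is not drawn from the documents.

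The cost is an amendment to three footnotes, plus one sentence if the option is taken. A cycle could be brought forward by at most 2 days instead of 7, so 5 days of early flexibility are lost. The late allowance is unchanged.
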